## **8.8 SAFETY ANALYSIS**

Patients who have taken at least one dose of Praxbind will be considered for the safety analysis. In general, safety analyses will be descriptive in nature and will focus on any suspected ADRs (serious and non-serious), serious AEs and AEs leading to death.

Additionally, physical examinations, vital signs, clinical laboratory test will be listed.

## **8.8.1 Adverse events**

### **Analysis of Adverse Events:**

All AEs captured in the eCRF will be listed for each patient and system organ class (SOC) and preferred term (PT) assigned to the AEs. The adverse events will be listed and analysed by taking the Overall count, counts as per SOC and PT, as per the relationship with drug and Seriousness category.

No imputation is planned for missing AE data except for missing onset dates which will be handled according to BI standard.

No adverse events of special interest (AESI) have been defined for this surveillance.

An AE is considered to be an ADR if either the physician who has reported the AE or the sponsor assesses its causal relationship as 'related'.

The incidence and grading of AEs will be tabulated by system organ class and preferred term. Adverse events will be categorized by serious adverse event (SAE), non serious adverse event, death or withdrawal. These categories will be further summarized by the causal relationship to study drug. An overall summary of the number and percentage of patients in each category will be presented in each category.

The following AE summary tables will be prepared:

- Overall Summary of AEs
- Summary of AEs by SOC and PT
- Summary of AEs by maximum severity (Intensity), SOC, and PT
- Summary of AEs related to treatment by SOC and PT
- Summary of Serious AE by SOC and PT
- Summary of deaths by SOC and PT
- Summary of Serious AEs related to treatment by SOC and PT
- Summary of non-serious AEs related to treatment by SOC and PT
- Summary of AEs causing discontinuation from study drug by SOC and PT

- Summary of AEs causing dose reduction of study drug by SOC and PT

The frequency of AEs/SAEs and ADRs will be tabulated by system organ class and preferred term.

The following list of Adverse Events will be considered under the category of Hypersensitivity and Thrombotic Events

➤ **Hypersensitivity:**

- Acute respiratory failure
- Anaphylactic reaction
- Anaphylactic shock
- Bronchospasm
- Circulatory collapse
- Erythema
- Generalised oedema
- Localised oedema
- Mouth ulceration
- Pneumonitis
- Pruritus
- Rash
- Respiratory arrest
- Respiratory distress
- Respiratory failure
- Scrotal oedema
- Shock
- Skin oedema
- Urticaria
- Wheezing

➤ **Thrombotic events**

- Ischemic Stroke
- Myocardial Infarction
- DVT only
- Pulmonary Embolism only
- DVT+ Pulmonary Embolism
- Systemic Embolism only
- Systemic Embolism + DVT

Multiple overlapping or adjacent AE occurrences of same AEs are collapsed into one AE event if all AE attributes are identical (patient number, LLT, outcome, therapy, intensity, action taken, seriousness, reason for seriousness, causal relationship).

Two AEs are considered to be time-overlapping if the start date of the second, later occurrence is earlier or equal to the end date of the first occurrence.

Two AEs are considered to be time-adjacent if the start date of the second, later occurrence is one day later than the end date of first occurrence.

After the collapsing the events to remove duplication and clarify any inconsistencies, the resulting data will form the basis for all reporting of AE data in the listing, table and figures.

Patients reporting more than one AE for a given MedDRA Preferred Term will be counted only once for that term using the most severe incident. Patients reporting more than one type of event within a SOC will be counted only once for that SOC. Any deaths, other SAEs, and other significant adverse events including those leading to premature discontinuation, will be separately identified.

Duration of AEs will be derived and presented in all listings.

AE Duration: (AE End date – AE Start date)+1. If date and time are not missing then the duration will be calculated in day and time.

AEs will be coded using the version 20.0 or higher of the Medical Dictionary for Regulatory Activities (MedDRA).

The grading of adverse events will be done by using Common Terminology Criteria for Adverse Events version 4 (CTCAE v4).

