### **7.2 IMPORTANT PROTOCOL VIOLATIONS**

This surveillance is mainly focused on prescription patterns of use of Praxbind in a clinical practice setting, with special focus on ADRs and fatal AEs. So in this surveillance per protocol (PP) analysis will not be considered. Hence, the iPV table will be included for completeness and also to demonstrate a level of quality (or adherence to the protocol).

The following table defines, but is not limited to, the different categories of important PVs:

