## **8.4 PRIMARY OUTCOME(S)**

Any suspected ADRs and fatal AEs; with special focus on hypersensitivity and thrombotic event, occurred within 7 days after Praxbind™ administration will be analysed for primary outcome results.

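### SAP 8.8.1: the lists that define the two special-focus categories omit the term 'hypersensitivity' and leave the counting of combined thrombotic events ambiguous

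*SAP*

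**What the plan says.** SAP 6.1 and 8.4 repeat the protocol's primary outcome (protocol 10.2.2.1): suspected ADRs and fatal AEs, "with special focus on hypersensitivity and thrombotic event, occurred within 7 days after" administration. SAP 8.8.1 then says what belongs to the two focus categories: "The following list of Adverse Events will be considered under the category of Hypersensitivity and Thrombotic Events". Two lists follow.

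- Hypersensitivity has 20 terms, running alphabetically from acute respiratory failure to wheezing.
- Thrombotic events have seven entries. Ischaemic stroke and myocardial infarction (MI) stand without qualification. The other five are DVT alone, "Pulmonary Embolism only", DVT with PE, "Systemic Embolism only" and "Systemic Embolism + DVT".

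The same section states: "No adverse events of special interest (AESI) have been defined for this surveillance". No MedDRA query is named for either category. On counting, 8.8.1 works by coded term: "Patients reporting more than one AE for a given MedDRA Preferred Term will be counted only once for that term".

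**The concern.** With no AESI definition and no named query, these lists are all that a programmer has for deriving the focus counts. Nothing in the lead-in marks them as examples. Elsewhere the SAP does mark an open list: its violation table in 7.2 "defines, but is not limited to, the different categories of important PVs". A literal term match is therefore a reasonable way to program 8.8.1, and it raises two problems.

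First, an event coded simply as hypersensitivity would not be flagged as hypersensitivity.

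Second, 'only' and '+' describe the set of events that one patient had. They are not coded terms, and they sit awkwardly with a rule that counts patients by preferred term. Someone must decide whether the seven entries are rows into which patients are sorted or merely a way of naming the events that belong. If that is decided after the data are seen, the choice can change the reported number. A report could then show no patient in a focus category while a listing shows one.

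**Working it through.** The documents give no figure on this point to reproduce. The check compares the list entries with the events they should catch.

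**Inputs.** The 20 hypersensitivity terms and seven thrombotic entries come from SAP 8.8.1. The maximum of 25 patients comes from protocol 10.4 and 10.8. The denominator is the treated set (SAP 7.3).

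**Hypersensitivity list.** Searching the 20 terms for 'hypersens' gives 0 matches. The nearest entries are anaphylactic reaction and anaphylactic shock, which are different coded terms.

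**Thrombotic list.** DVT, PE and systemic embolism (SE) can occur in 2^3 − 1 = 7 non-empty combinations. The table matches each one to the five entries that concern them.

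| Patient's events | Rows, '+' exact | Rows, '+' inclusive | Simple membership |
|---|---|---|---|
| DVT | DVT only | DVT only | counts |
| PE | PE only | PE only | counts |
| SE | SE only | SE only | counts |
| DVT, PE | DVT + PE | DVT + PE | counts |
| DVT, SE | SE + DVT | SE + DVT | counts |
| PE, SE | none | none | counts |
| DVT, PE, SE | none | both '+' rows | counts |
| Covered | 5 of 7 | 6 of 7 | 7 of 7 |

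Adding stroke and MI gives 2^5 − 1 = 31 combinations. Those two entries are unqualified, so each of the 31 − 7 = 24 combinations that contain either one has a row. The gaps stay at two (exact) or one (inclusive). These are counts of patterns, not probabilities; the documents give no event rates.

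**Weight of one patient.** One patient is 1/25 = 4.0 percentage points, and 1/N is larger if fewer are treated. Protocol 10.6.1 lists 95% CIs among the descriptive statistics, but neither document names a method. Exact (Clopper-Pearson) limits are used here.

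- 0/25: lower limit 0; upper limit 1 − 0.025^(1/25) = 13.7%.
- 1/25: lower limit 1 − 0.975^(1/25) = 0.1%; upper limit = 97.5% quantile of Beta(2, 24) = 20.4%.

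**The case against.** The strongest reply is that the lead-in to the lists is about membership. On that view, a patient with PE and systemic embolism has two thrombotic events and is counted, and the gap disappears. This stands as far as it goes: a reader might infer that such a patient is necessarily lost, and the documents do not support that. They support only that the labels fit patient-level rows, the lead-in fits membership, and nothing chooses between them.

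The closed-list inference can also be challenged. The open-ended phrase in 7.2 belongs to a section with another purpose, and a sensible analyst would hardly leave an event coded hypersensitivity out of a category of that name. Both remarks are fair, but they rely on the analyst departing from the list as written.

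Three further inferences are tempting and should not be drawn.

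- That the absence of angioedema is an error. It is not among the 20 terms, but whether it belongs is a clinical judgement that neither document makes.
- That one patient appearing in two thrombotic rows is a defect. Overlap is harmless if rows are declared non-exclusive, and the unqualified stroke and MI entries already allow it.
- That the 7-day focus analysis is not planned, because none of the ten AE tables named in 8.8.1 is by focus category or limited to 7 days. SAP 8.4 commits to analysing the outcome within 7 days. The missing table layout is a separate matter from the content of the lists.

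Finally, the practical reach is small. Protocol 12.2 collects only ADRs and fatal AEs, so the thrombotic gap needs one patient with both embolic events reported on those terms. That is correct, and it limits the weight of the point.

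**Conclusion.** The point holds as a minor defect of specification. Applied literally, SAP 8.8.1 leaves an event coded hypersensitivity out of the hypersensitivity category. It also does not settle whether patients with PE plus systemic embolism, with or without DVT, are counted in the thrombotic breakdown.

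This rests on three assumptions: the public text contains no other definition of the categories; an event can be coded under the term hypersensitivity; and the lists are applied as written. The thrombotic part depends further on the row reading.

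No event disappears from the study. The overall ADR and fatal-AE outcome, the tables by system organ class and preferred term, and the patient listings (SAP 8) are unaffected, and the analysis is descriptive with no hypothesis (protocol 10.8). The 4.0-point shift is the weight of any single patient at 25, not a measure of how likely a miscount is.

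**What to change.** Amend SAP 8.8.1 before database lock:

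1. Add 'hypersensitivity' to the list, which takes it from 20 to 21 terms. Ask the sponsor's medical reviewer to confirm whether other terms, such as angioedema, belong.
2. Replace the 'only' and '+' entries with a count of patients with any thrombotic event, followed by non-exclusive rows for ischaemic stroke, MI, DVT, PE, systemic embolism and other.

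The cost is a wording change and light programming, with no new data and no effect on sites or patients. The downside is that component rows may sum to more than the number of patients. The row for any thrombotic event gives the patient count, and a footnote can say so.

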### **8.8.2 Laboratory data**

Listings of laboratory results and laboratory test performance date prescribed for each patient. Values outside of the laboratory's reference range (i.e., those with high or low values) will be flagged in the laboratory listings.

Laboratory tests with continuous results will be summarized descriptively. For categorical data will be summarized using frequency and proportion.

Frequency count with percentage for possibly clinically significance abnormalities will be presented separately.

### **8.8.3 Vital signs and Physical Examinations**

Vital sign and physical examination results (including pulse rate, systolic and diastolic blood pressure, height, weight) will be listed by patient as baseline characteristics. Also, continuous results of vital sign and physical examinations will be summarized descriptively (n, mean, SD, median, Q1, Q3, minimum, and maximum) as baseline characteristics.

### **8.8.4 ECG**

This section is not applicable as no ECG data are collected.

### **8.8.5 Others**

This section is not applicable as no other analysis is needed.

## **11 HISTORY TABLE**

**Table 10: 1 History table**

Version	Date (DD-MMM-YY)	Author	Sections Changed	Brief description of change
Final 1.0	11-Jul-2018		None	This is the Final V1.0 of TSAP with necessary information for trial conduct

